Fibrotic livers have reduced elasticity due to the deposition of fibrous tissue in the hepatic parenchyma. TE gives a 'liver stiffness measurement' (LSM) using pulsed-echo ultrasound as a surrogate marker of fibrosis. The LSM correlates well with the degree of hepatic fibrosis in a range of liver diseases, including NAFLD, hepatitis B, hepatitis C and in patients treated with methotrexate²². In a study of 246 patients with biopsy-proven NAFLD, TE achieved high AUROCs for the detection of \geq stage 2 fibrosis, \geq stage 3 fibrosis and cirrhosis (0.84, 0.93 and 0.95, respectively) and performed better than a number of simple non-invasive scores in the staging of fibrosis. In that study, TE had a high NPV of 96% for \geq stage 3 fibrosis at a cut-off of 7.9 kPa but only modest PPV (52% at 7.9 kPa and 72% at 9.6 kPa)²³. A low LSM reliably excludes advanced fibrosis, but the optimum cut-offs for clinical use are yet to be determined. Previous observational studies looking at the prevalence of liver fibrosis and advanced liver fibrosis used LSM >7 kPa and LSM >9.5 kPa as their cut-off values³⁻⁵. However, there are significant limitations to using TE. Results may be invalid in those with central obesity (BMI >35 kg/m²) or type 2 diabetes²⁴. For obese patients, the Fibroscan XL probe has been developed that is associated with fewer LSM failures (1.1% vs16%) than the M probe and was accurate for the diagnosis of \geq F2 fibrosis and cirrhosis (AUROC 0.83 and 0.94, respectively)²⁵. However, even with the XL probe, 10% of patients with a BMI >28 kg/m² have a difference of ≥ 2 fibrosis stages between TE and liver biopsy²⁶.

Despite its limitations, the usefulness of TE in detecting liver fibrosis in patients with psoriasis has been demonstrated and TE is increasingly recommended to be used in monitoring patients taking methotrexate ^{4, 21}.

9. Objectives

Primary objective To determine the prevalence of liver fibrosis in patients with psoriasis (LSM >7.9kPa, >7.0 kPa, > 9.5kPa) and to evaluate the relationship between the cumulative dose of methotrexate and liver fibrosis in patients with psoriasis.

Secondary objectives

1. To evaluate the relationship between other liver fibrosis risk factors and non-invasive markers of liver fibrosis in patients with psoriasis using univariate analysis.

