Cardiac disease (Heart failure, Cardiac arrhythmias, Stroke , Coronary artery disorders, Angina , Myocardial infarction), Vascular diseases (Hypertension, Peripheral vascular disorders, Deep vein thrombosis, Pulmonary embolism , Disorders of metabolism and nutrition (Diabetes mellitus, Impaired glucose tolerance , Dyslipidaemia , Endocrine diseases (Thyroid disease), Nervous system disorders(Demyelinating diseases ,Epilepsy) , Respiratory, thoracic and mediastinal disorders (Asthma, COPD) , Renal and urinary tract diseases (Chronic renal failure), Hepatobiliary diseases (Viral hepatitis infection, Other liver disease), Gastrointestinal diseases (Peptic ulcer), Gastrointestinal inflammatory conditions (Crohn’s disease, Ulcerative colitis), Psychiatric diseases (Depression, Anxiety), Infections and infestations (Tuberculosis). Immune system disorders, Skin and soft tissue disorders (Psoriatic arthritis (Diagnosis of PSA by a rheumatologist? And Year of diagnosis), Other types of cancers: Skin cancers (Non-melanoma skin cancer, Squamous cell, carcinoma, Basal cell carcinoma) Melanoma skin cancers and pre-

cancerous skin lesions (Melanoma skin cancer, Melanoma in situ, Bowen disease, Actinic keratosis, Keratoacanthoma)

- Duration on methotrexate in months, cumulative dose of methotrexate
- UV Therapy– (yes/No), duration and type, response
- Any current systemic drug, Oral PUVA or biologics for psoriasis, Small molecule immunomodulator therapy for psoriasis (Apremilast or dimethyl fumarate) – dose, frequency and date started
- All previous systemic or biologics or oral PUVA, small molecule immunomodulator therapy for psoriasis – start and stop dates and stop reason
- Any other systemic drug or biologic drugs (dose and frequency) and durations with start dates and stop dates and duration
- Current medications and start dates – including pimecrolimus or tacrolimus
- Folic acid: Duration and Frequency
- Blood tests: HBA1C, Fasting glucose (if available), Lipid profile including, Triglycerides, HDL cholesterol, AST, ALT, Abnormal AST in the past year, Abnormal ALT in the past year, Worse ever AST/ALT, Platelets, Procollagen three peptide (PIIINP), Albumin.
- Previous liver ultrasound report, Previous liver biopsy report

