11.5. Eligibility Criteria

11.5.1 Inclusion Criteria

- Adults \geq 18 years of age
- Ability to consent
- Chronic plaque Psoriasis diagnosed by a dermatologist with a PASI \geq 5

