11.5.2 Exclusion Criteria

- Pregnancy
- Potential participants who may have difficulties in adequately understanding written or verbal information in English

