11.13. Analysis Methods

All of the data will be assembled in a spreadsheet that will be designed and checked by our statistical collaborators.

The analysis will be performed including all patients and then the group will be divided based on the PASI score (PASI >10 and PASI <10) and analysis of the separate groups will be performed.

We will calculate the prevalence of liver fibrosis (the proportion of the population affected by liver fibrosis) by dividing the number of participants with liver fibrosis in the study population by the total number of people in study population.

For the analyses we will perform these 3 times using the 3 different cut off values for liver stiffness measurements of 7Kpa, 7.9Kpa and 9.5Kpa. There is currently no consensus as to which value is most appropriate. We will therefore analyse using all three.

Regression analyses will be carried out, the results of which will be used to inform a power calculation for future research.

- Logistic regression will be used to consider the association between liver fibrosis (yes/no) and methotrexate dose (continuous).
- Linear regression will be used to consider level of liver fibrosis (continuous i.e. independent of cut offs) and methotrexate dose (continuous).
- Regression models will also be used to investigate the relationship between other risk factors (e.g. BMI, waist circumference, alcohol consumption etc.) and liver fibrosis.

Analysis will be carried out in STATA 15.

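### Participants with viral hepatitis or another known liver disease stay in methotrexate regressions that name dose as the only predictor, so the methotrexate association can be biased in either direction

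*Protocol*

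**What the plan says.** **Eligibility.** Section 11.5.1 sets no condition on the liver. Section 11.5.2 has two exclusions: pregnancy, and "Potential participants who may have difficulties in adequately understanding written or verbal information in English".

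**Data collected.** The comorbidity list in section 10 includes "Hepatobiliary diseases (Viral hepatitis infection, Other liver disease". It asks whether the patient ever had or needed treatment for the illness, and the year of onset. The CRF in the appendix gives viral hepatitis one line and all other liver disease one undivided line.

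**Analysis (section 11.13).**
- Analysis set: "The analysis will be performed including all patients and then the group will be divided based on the PASI score".
- Prevalence: "dividing the number of participants with liver fibrosis in the study population by the total number of people in study population".
- Methotrexate, binary outcome: "Logistic regression will be used to consider the association between liver fibrosis (yes/no) and methotrexate dose (continuous". A linear regression of continuous LSM on dose is described in the same way. Neither names another predictor or a restriction.

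**Outcome measure.** Section 8, on transient elastography, says LSM correlates with fibrosis across several liver diseases, "including NAFLD, hepatitis B, hepatitis C and in patients treated with methotrexate".

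**The concern.** LSM does not identify the cause of fibrosis. A participant with hepatitis-related fibrosis can exceed all three cut-offs for a reason that has nothing to do with methotrexate. In a regression with dose as the only predictor this does no systematic harm if such participants are spread evenly over dose. If they cluster at low, zero or high dose, their fibrosis is attributed to dose.

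The protocol's own account makes clustering plausible. Section 8 says that other agents are used where methotrexate is not appropriate, that liver toxicity has been a long-standing worry, and that confounding has kept the drug's role unclear. It does not say how liver disease relates to dose in this clinic.

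At stake is the methotrexate half of the primary objective. Section 11.13 also feeds the regression results into the power calculation for the later study, so a biased estimate would be carried forward.

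**Working it through.** The protocol gives no figure for the share of participants with other liver disease or for their fibrosis rate, so there is no figure of its own to reproduce. The 250 in section 11.6 is a pilot size without stated inputs and is not disputed.

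**Inputs from the protocol.** N = 250, and at least 100 ever-users of methotrexate (11.6), taken here as 100 ever-users and 150 never-users. Background prevalences quoted in section 8: 8.1%, 11% and 14.1%.

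**Assumptions.** Prevalence above a cut-off in the other participants, p = 10%. Number with other liver disease, k = 5 to 10 (2-4% of 250). Proportion of those above the cut-off, q = 30-60%. No true methotrexate effect. Dose is reduced to ever/never for the arithmetic.

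**1. All affected participants among never-users.** Never-user prevalence = [(150 − k) × 0.10 + k × q] / 150; ever-user odds = 0.10/0.90 = 0.1111.
- k = 5, q = 0.3: (14.5 + 1.5)/150 = 0.1067, odds 0.1194, OR = 0.1111/0.1194 = 0.93
- k = 5, q = 0.6: (14.5 + 3)/150 = 0.1167, odds 0.1321, OR = 0.84
- k = 10, q = 0.3: (14 + 3)/150 = 0.1133, odds 0.1278, OR = 0.87
- k = 10, q = 0.6: (14 + 6)/150 = 0.1333, odds 0.1538, OR = 0.72

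**2. All among ever-users.** Ever-user prevalence = [(100 − k) × 0.10 + k × q] / 100.
- k = 5, q = 0.3: 0.11, odds 0.1236, OR = 0.1236/0.1111 = 1.11
- k = 10, q = 0.6: 0.15, odds 0.1765, OR = 1.59

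**3. Spread evenly.** With k = 10 and q = 0.6, 4 in the 100 and 6 in the 150: (9.6 + 2.4)/100 = 0.12 and (14.4 + 3.6)/150 = 0.12, so OR = 1.00.

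**4. Other inputs.** With the three background prevalences as p and q = 30-50%, the two extremes over all combinations are 0.84 and 1.29 at a 2% share, and 0.67 and 1.75 at a 5% share.

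**5. Against sampling error.** With 10/100 and 15/150 events, SE(log OR) = √(1/10 + 1/90 + 1/15 + 1/135) = 0.43. The extremes in steps 1 and 2 are ln 0.72 = −0.33 and ln 1.59 = 0.46, so the bias reaches at most about one standard error.

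**6. Prevalence.** Observed = (1 − f) × 0.10 + f × q, with f = k/250.
- f = 0.02, q = 0.3: 0.098 + 0.006 = 10.4%
- f = 0.04, q = 0.6: 0.096 + 0.024 = 12.0%

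The shift is 0.4-2.0 points, and these participants supply 0.006/0.104 = 5.8% to 0.024/0.120 = 20% of cases. The 95% half-width at 10% is 1.96 × √(0.1 × 0.9/250) = 3.7 points.

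The linear model uses LSM itself, so a very high value at one end of the dose range can have more leverage than a yes/no outcome allows. That effect depends on LSM values the protocol does not give, and it is not quantified here.

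**The case against.** **The prevalence is all-cause.** A reader might infer that the headline prevalence is wrong because it counts fibrosis of unrelated origin. The documents do not support this. The objective is fibrosis in patients with psoriasis, and 11.13 divides all affected participants by all participants. For that target, inclusion is right. This objection stands in full.

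**The direction is unknown.** It is tempting to conclude that the methotrexate effect will be pulled towards null or protective. That requires known liver disease to steer patients away from methotrexate, and section 8 does not name liver disease as a reason why the drug may be inappropriate. Steps 1 to 3 show that the bias can run either way or vanish. The comorbidity question also covers resolved illness, so the 30-60% may be too high. This stands as a limit on size and direction; it does not remove the exposure to bias.

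**Causes can be separated from other data.** It would be too strong to say the CRF makes this impossible. Viral hepatitis has its own line, and ultrasound and biopsy reports, AUDIT score, alcohol history, BMI, waist and metabolic syndrome are collected. They identify the cause only in part, because imaging and biopsy reports exist only for some participants and risk factors are not a diagnosis.

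**This is a pilot, with adjustment deferred.** Multivariable work belongs to the later study, obesity and alcohol are also unadjusted here, and a sensitivity analysis could sit in an SAP that is not shown. Liver disease may also be examined as a risk factor in its own right, since the list in 11.13 is open. This is fair as to priority. A separate univariate model does not correct the dose coefficient, however, and the protocol already fixes the analysis set, the named predictor and the CRF line. If an SAP already contains the restricted analysis, only the CRF part remains.

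**Conclusion.** The point holds for the methotrexate association, not for the prevalence. Known liver disease of unrelated cause is eligible, recorded and left unhandled in regressions whose outcome also responds to it.

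Under the stated assumptions and no true effect, 5 to 10 such participants move the crude odds ratio to 0.72-0.93 if all are never-users and to 1.11-1.59 if all are ever-users; an even spread leaves it at 1.00. The extremes need every affected participant in one group, and even they amount to no more than about one standard error at this sample size. The all-cause prevalence is correctly defined, and its shift of 0.4-2.0 points is below the half-width of about 3.7.

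This is a low-cost improvement that protects half of the primary objective and the later power calculation. It is not a flaw that invalidates the study, and the documents give no ground for excluding these patients from enrolment.

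**What to change.** **Section 11.13.** Keep the all-patient analyses as the main ones. Add that the methotrexate logistic regressions (at each of the three cut-offs) and the linear regression will be repeated without participants who have recorded viral hepatitis or another liver disease that is neither metabolic nor alcohol-related, and reported beside the all-patient results. Fatty and alcohol-related disease stay in, because their risk factors are among those the study examines. Showing prevalence both ways is optional and descriptive.

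**CRF.** Split Other liver disease into fatty liver, alcohol-related, and other (specify). This is best done before data collection, since later reconstruction would depend on whichever reports exist.

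**Cost.** One CRF subdivision, one repeated set of regressions, and a restricted set smaller by a few participants (5 to 10 of 250 under the assumptions above). Eligibility and recruitment do not change.

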11.1. Quantitative outcome measure

- The prevalence of liver fibrosis in patients with psoriasis (LSM >7.9kPa)
- Assessment of risk factors and non-invasive markers of liver fibrosis

11.2. Qualitative outcome measures

None

11.3. Definition of end of study

Recruitment target achieved.

11.4. Study population

Patients with moderate to severe chronic plaque psoriasis attending the dermatology department at Royal Victoria Infirmary, Newcastle.

11.5. Eligibility Criteria

11.5.1 Inclusion Criteria

- Adults \geq 18 years of age
- Ability to consent
- Chronic plaque Psoriasis diagnosed by a dermatologist with a PASI \geq 5

11.5.2 Exclusion Criteria

- Pregnancy
- Potential participants who may have difficulties in adequately understanding written or verbal information in English

11.6. Sampling strategy

Total sample size: 250 (can be increased to up to 500).

As this is a pilot study, this should be an adequate sample to test recruitment and the estimate effect sizes to include in a formal statistical power calculation for a planned larger study.

We are interested to recruit a mix of patients receiving different types of treatment including phototherapy and biologics. We will aim to recruit at least 100 patients who are receiving or have previously received methotrexate.

We will compare our study population to BADBIR population to ensure we demonstrate that our sample is representative.

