Number of study sites	One (the Newcastle upon Tyne Hospitals NHS Foundation Trust)
Study population size	250
Study duration	2 years

7. Introduction

Patients with psoriasis appear to have higher rates of liver fibrosis in comparison to the general population. The higher rates of risk factors for liver fibrosis such as obesity, alcohol and diabetes are important; however there have been concerns that methotrexate can contribute to liver fibrosis. Ever since methotrexate has been used to treat psoriasis there have been concerns over the risk to liver health. Until the 1990s liver biopsies were recommended pre and during MTX therapy. Despite the increasing importance of biologic therapies, methotrexate remains the most commonly used systemic agent in the UK. The majority of patients needing systemic therapy will try methotrexate first as per NICE guidance.

This study aims to investigate the prevalence of liver fibrosis in a group of patients with psoriasis by measuring liver stiffness measurement (LSM) using Transient Elastography (TE), now increasingly used for monitoring of liver fibrosis. The previous standard to monitor liver fibrosis was liver biopsy but concerns over morbidity and mortality along with sampling error have led to a decline in this test being performed. In addition to measuring liver stiffness, the cumulative methotrexate dose and other important factors including BMI, waist circumference and alcohol intake will be recorded. A univariate analysis will be performed to investigate the relationship between all measured risk factors and LSM.

The ultimate goal is to use the prevalence data to perform a power calculation to determine the number of participants required to conduct a study to determine which factors can predict the risk of liver fibrosis. Increasingly experts believe that other risk factors for liver fibrosis such as obesity and alcohol intake may be more important than methotrexate. We want to determine whether or not methotrexate is an independent risk factor for liver fibrosis in patients with psoriasis and if so whether we can predict which populations are most at risk from negative side effects of methotrexate. Using this data a risk prediction model can be built to allow optimal and safe prescribing of methotrexate.

8. Background

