2. To perform a power calculation to determine number of participants required for a large multivariable analysis to investigate factors influencing liver fibrosis and determine which risk factors are most important in the development of live fibrosis.

Primary outcome To determine the prevalence of liver fibrosis in patients with psoriasis (LSM >7.9kPa, >7.0 kPa, > 9.5kPa) and to evaluate the relationship between the cumulative dose of Methotrexate and liver fibrosis in patients with psoriasis.

10. Method and Study Design

The study will be a cross sectional design. Patients with psoriasis with a PASI score of at least 5 and duration of at least 1 year will be invited to join the study.

All of the data that we are interested in is recorded as part of standard clinical care and we do not want to repeat measurements unnecessarily. We will therefore accept values for blood tests that have been recorded within 6 months of patient recruitment and LSM values that have been recorded within 12 months of recruitment to the study.

For patient severity scores and assessments of clinical data such as BMI, these will be collected at the time of recruitment.

The following data will be recorded for each patient:

- Patient demographics: Age, Gender, Ethnicity Socioeconomic status.
- Disease severity: Duration of psoriasis, Age of onset of psoriasis), Year of diagnosis (best approximation), Year first seen by a dermatologist, PASI at recruitment, Worse ever PASI, DLQI at recruitment, worse ever DLQI, Family history of psoriasis (first degree relative such as parent, sibling or child).
- Characteristics: Height and Weight, Body Mass Index (BMI), Waist circumference, smoking status, alcohol intake questionnaire and AUDIT score, Blood pressure , skin type and skin cancer risk factors.
- Liver stiffness measurements: Value, >7.9kPa (yes/no), > 7kPa (yes/no), > 9.5kPa (yes/no).
- Alcohol related questions: AUDIT score, Average alcohol intake in the last year (units per day or units per week)*, A history of sustained excessive alcohol consumption of > 35 units/week for females or > 50units per week for males for more than 1 year, A history of excessive alcohol consumption (>14 units/day for both) – document the average units/day or week and the duration of alcohol, A history of alcohol dependence.
- Comorbidities –has the patient ever had or required treatment for the following illnesses and year of onset of illness:

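### The larger study's power calculation would draw on this pilot's univariate effect estimates, which are imprecise and answer a different question, while the Introduction names prevalence as the input

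*Protocol*

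**What the plan says.** Secondary objective 2 (sections 6 and 9) is "To perform a power calculation to determine number of participants required for a large multivariable analysis". Three places bear on what will feed that calculation.

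- **Section 11.6:** "Total sample size: 250 (can be increased to up to 500"; as a pilot, this size is called adequate for trying out recruitment and to "estimate effect sizes to include in a formal statistical power calculation". The section gives no precision target, alpha, power or effect size.
- **Section 11.13:** "Regression analyses will be carried out, the results of which will be used to inform a power calculation for future research". The models listed are logistic regression of fibrosis (yes/no) on continuous methotrexate dose, linear regression of continuous LSM on dose, and models for other risk factors. No adjusted model is described.
- **Section 7 (Introduction):** "The ultimate goal is to use the prevalence data to perform a power calculation". Here the input is prevalence, not effect size.

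On the type of analysis, the Introduction says "A univariate analysis will be performed to investigate the relationship between all measured risk factors and LSM", and secondary objective 1 likewise specifies univariate analysis. The same Introduction says that the wider aim is to learn whether methotrexate is an independent risk factor, and that obesity and alcohol may matter more.

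**The concern.** The power calculation is a stated deliverable. Sections 11.6 and 11.13 supply it with effect estimates from this pilot, and the Introduction supplies it with prevalence. The choice matters because required sample size varies with the inverse square of the effect. A noisy effect estimate therefore gives a much noisier sample size.

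There is also a mismatch of target. A crude association between dose and fibrosis is not the quantity that a multivariable study of independent effects must detect, and recruiting more pilot patients would not cure that. The larger study could end up badly underpowered or needlessly large, although section 11.6 calls the sample adequate for this use.

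**Working it through.** **1. The plan's own figure.** With no alpha, power, effect or margin stated, 250 can be neither reproduced nor refuted. For prevalence, 1.96 × √(p(1−p)/250) gives a 95% half-width of 3.4, 3.9 or 4.3 percentage points at p = 8.1%, 11% or 14.1%.

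**2. Inputs.** From the protocol: N = 250, up to 500 (section 11.6); prevalences of 8.1% (>9.5 kPa), 11% (>7 kPa) and 14.1% (>9.5 kPa, severe psoriasis) from the studies cited in section 8. Assumed: two-sided alpha 0.05, power 80%, true odds ratio (OR) per SD of dose of 1.3, 1.5 or 2.0.

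**3. Events.** 250 × 0.081 = 20.25; 250 × 0.11 = 27.5; 250 × 0.141 = 35.25.

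**4. Precision of the pilot effect.** SE(log OR per SD) ≈ 1/√(N p(1−p)). At 11% this is 1/√(250 × 0.11 × 0.89) = 0.202, so the 95% interval runs from the estimate divided by 1.49 to the estimate multiplied by 1.49. The factor is 1.58 at 8.1% and 1.43 at 14.1%.

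**5. Effect on planned N.** Needed N = (1.960 + 0.842)² / (p(1−p)b²), with b the true log OR. For OR 1.5 at 11%: 7.849 / (0.0979 × 0.4055²) = 488. Pilot estimates were drawn from Normal(b, SE), 400,000 draws per scenario, and N was planned from each point estimate. At N = 250 and 11% prevalence:

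| True OR per SD | Needed N | Planned ÷ needed N, 10th–90th percentile | Planned below half of needed |
|---|---|---|---|
| 1.3 | 1165 | 0.25–20 | 30% |
| 1.5 | 488 | 0.37–7.3 | 20% |
| 2.0 | 167 | 0.53–2.5 | 8% |

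Planned N falls below needed N about half the time in each row.

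**6. Other conditions.** With OR 1.5 and N = 250, the range is 0.33–10.9 at 8.1% prevalence, 0.40–5.5 at 14.1%, and about 0.47–3.5 at an assumed 25%. With N = 500 at 11% it is 0.47–3.3. For the linear model of LSM on dose at N = 250, it is 0.30–14 at an assumed correlation of 0.10 and 0.51–2.8 at 0.20.

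**7. Univariate input for a multivariable target** (assumed values).
- A crude OR of 1.5 that becomes 1.3 after adjustment needs (ln 1.5 / ln 1.3)² = (0.4055/0.2624)² = 2.4 times the N.
- An R-squared of 0.2 to 0.4 between dose and the other covariates multiplies N by 1/(1−R²), that is 1.25 to 1.67.
- At OR 1.5, 11% and N = 250, these raise the chance that the plan is too small. For R-squared 0.2, the plan is too small if the estimate exceeds 0.4055/√1.25 = 0.363, and Φ((0.4055 − 0.363)/0.202) is about 58%. For R-squared 0.4 the threshold is 0.314 and the chance about 67%. For the attenuation to 1.3 the threshold is 0.262 and the chance about 76%.

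**8. Prevalence as the only uncertain input.** With a pre-set effect, planned N varies as 1/(p(1−p)). Across the 95% interval at 11% and N = 250 (7.1% to 14.9%), it moves only from 0.77 to 1.48 times. At 8.1% the range is 0.73 to 1.66, and at 14.1% it is 0.81 to 1.37.

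The normal approximation is rough with 20 to 35 events. Section 11.6 asks for only 100 or more patients ever on methotrexate, so up to 150 of 250 could have zero dose. The ranges in steps 5 and 6 probably understate the uncertainty.

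**The case against.** **The text does not say that the point estimate goes straight into the calculation.** Sections 11.6 and 11.13 speak of including and informing. Neither rules out a confidence limit, a target effect or variance inflation, and such detail can be left to an SAP or to the later study's protocol. This stands: a reader might infer a mechanical plug-in, but the documents do not fix one. What they do fix is the source (this pilot's effects), its univariate character, and the claim that the sample is adequate for it.

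**The Introduction already names the better input.** It does, and one should not read its ultimate goal as using effect sizes. But it conflicts with sections 11.6 and 11.13, which is a reason to revise rather than a defence.

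**The event count may be low.** The cited prevalences mix populations and cut-offs. If 14.1% above 9.5 kPa applied here, the lower cut-offs would give at least 35 events. The permitted 500 and the linear model also narrow the range at moderate effects. All of this stands, and step 6 shows the gain. None of it addresses the univariate–multivariable mismatch.

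**The error runs both ways.** A reader might infer that the larger study would usually be too small. Sampling error alone makes that roughly an even chance. The further tilt depends on assumed attenuation or covariate correlation, and negative confounding could reverse it.

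**Conclusion.** The point holds in a limited form. The protocol gives two different inputs for the same power calculation. The one in sections 11.6 and 11.13 is unsound as a design effect, because it is described as univariate where the target is adjusted, and because 20 to 35 events cannot fix it closely. For true odds ratios per SD up to about 1.5, a plan based on the point estimate at N = 250 could be wrong several-fold. For an odds ratio of 2.0, or for 500 patients at 1.5, the error is mostly within two- to threefold. These sizes rest on assumed effects, alpha, power, R-squared and attenuation, none of which the protocol states.

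It would go too far to conclude that 250 is inadequate for this study or that its results are compromised. The prevalence estimate is unaffected, and the consequence falls on the planning of the next study.

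**What to change.** In sections 11.6 and 11.13 and in secondary objective 2, state that the larger study will be powered on a pre-set smallest important adjusted effect, for example an odds ratio per gram of cumulative methotrexate. Take from this pilot only the prevalence at each cut-off, the variability of LSM, the dose distribution, and the R-squared of dose on the other covariates. Align the Introduction with this.

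If a pilot effect is used at all, use the adjusted estimate and show the planned N across its confidence interval. In section 11.6, limit the claim of adequacy to testing recruitment and estimating these nuisance quantities.

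The cost is wording and one extra regression of dose on covariates that are already collected; no new data are needed. The downside is that the planned N may be larger than a pilot point estimate would suggest.
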